## ***MRI and Connectivity:***

### **MRI Data Collection (Baseline and Week 32).**

Before treatment begins and at the 6 month follow-up appointment (week 32), subjects will participate in an fMRI cue exposure session (Claus et al., 2011). Participants who are determined eligible to have an MRI scan will undergo a structural scan, using a Siemens 3T Trio, followed by a functional MRI scan that involves alcohol cue exposure. Our cue procedure is consistent with NIAAA guidelines and less risky than previous studies that have examined this mechanism in a sample receiving treatment (e.g., Myrick et al., 2008; Spagnolo et al., 2014; see protection of human subjects section). **Structural MRI (sMRI):** We will acquire a high-resolution protocol sufficient to permit accurate tissue classification and anatomical parcellation. For optimal contrast between gray matter (GM), white matter (WM) and cerebral spinal fluid (CSF) at 3T, we will use a multi-echo MPRAGE (MEMPR) sequence with the following parameters: TR/TE/TI = 2300/2.74/900 ms, flip angle = 8°, FOV = 256x256 mm, Slab thickness = 176 mm, Matrix = 256x256x176, Voxel size = 1x1x1 mm, Number of echos = 4, Pixel bandwidth = 650 Hz, Total scan time = 6 min. **Functional MRI (fMRI) – Cue-Elicited BOLD:** fMRI scans will be collected with single-shot full k-space echo-planar imaging (EPI) with ramp sampling correction using the intercommissural line (AC-PC) as a reference (TR: 2.0 s, TE: 27ms,  $\alpha$ : 70°, matrix size: 64 × 64, 32 slices, voxel size: 3 × 3 × 4 mm^3). Image-based higher order automatic shimming will be employed. FMRI data will be acquired with a 32-channel coil. Scanner instability and signal-to-noise ratio during fMRI scanning on a phantom will be monitored weekly throughout the project period. Automated analysis of scanner instability with the Weiskoff method is routinely performed. We have used our alcohol cue task successfully in over 600 individuals (Claus et al., 2011). It is reliable and well validated. The task compares the taste of an individual's favorite alcoholic beverage with a sweet, appetitive control taste (litchi juice). The task was designed to minimize movement by only administering 1 ml of each beverage through Teflon tubing that is attached to a computer controller gustometer, over each 24 second trial. It is important to note that the total amount of the alcoholic beverage is only 12 ml (less than a teaspoon). The task itself involves a block design with twelve pseudorandomly ordered alcohol and control trials that are presented in two consecutive runs. In order to examine whether the effects of MBRP differ from those of RP, we will calculate the signal change for alcohol minus the control condition in the precuneus, putamen, and anterior cingulate and use the signal in these regions of interest (ROIs) in the structural equation models (see analysis section).

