### **MRI Scan I**

All subjects who are eligible will undergo a structural scan, using a Siemens 3T Trio, followed by an fMRI scan that involves alcohol cue exposure. Female participants will be asked to take a

pregnancy test free of charge and must have a negative result in order to continue with participation in the study. Female participants may opt out of the urine pregnancy test and sign a waiver (one of the standard INC MRI scanning forms) indicating they understand that the risks associated with MRI and unborn fetuses is unknown and that they are confident that they are not currently pregnant.

The research assistant will go over the contraindications for fMRI screening form again with the participant to ensure that eligibility has not changed since the phone screen; if there is any question that a participant might not be safe to go into the scanner the appointment will be cancelled and rescheduled if possible.

Prior to going into the MRI scanner, the MRI technologist on duty will ask participants to remove all jewelry and metal objects from their pockets. Participants will be required to change into scrubs to prevent any possible risk from metallic objects or decorations in their clothing. Eligible participants will be escorted to a changing room where they will be asked to change into the hospital scrubs provided, and to lock up their belongings in the locker.

A trained MRI technician will position participants in the scanner and ensure that all safety procedures are followed. In an MRI scan, the subject lies down on a table and is placed into a long donut-shaped magnet. A specially designed coil will be placed around the head to provide better images (as is done with standard clinical examinations). As the MRI scan is performed, the subject will hear loud rattling and knocking noises that are normal for a MRI scan.

During the scanning session, we will acquire anatomical images for subsequent analysis as well as functional images during an alcohol cue task. The alcohol cue task compares the taste of an individual's favorite alcoholic beverage with a sweet, appetitive control taste (litchi juice). Subjects will be administered 1 ml of each beverage through Teflon tubing that is attached to a computer controller gustometer, over each 24-second trial. The total amount of the alcoholic beverage is only 1 ml (less than a teaspoon).

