### **Exposure to Alcohol.**

During the fMRI scan at baseline and the second follow-up visit, participants are exposed to less than a teaspoon of an alcoholic beverage, there is a risk that participants may experience an urge to drink or it might cause cravings or anxiety. This risk is particularly relevant during the second MRI scan because many patients may have established abstinence or reduced their alcohol consumption substantially.

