### **Exposure to Alcohol.**

During the fMRI session, participants may experience a reaction to the alcohol presented to them during the scan. Such a reaction might manifest as craving or anxiety. These effects are almost always only temporary. We have used the same cue exposure task in over 600 participants; many of who were treatment-seeking patients who had established some measure of abstinence (required to be in our studies) prior to scanning. We have not observed any adverse effects from our cue exposure protocol in these individuals. It is important to understand that the entire task uses less than 1 tsp of an alcohol beverage. The consent form clearly notes that the cue exposure session takes place at baseline and at the second follow-up session (week-32) and clearly notes that patients can opt out of the cue exposure part of the study. The patients will be reminded again about the option to opt out of the MR scan. As we have done previously, we will conduct an assessment with each participant after the cue exposure session to determine whether there is any residual craving or anxiety. We also allow each patient to process his or her reaction to the alcohol cues with a therapist before leaving the experiment. Thus, the therapist and study staff will know immediately if there is an adverse reaction to the cues. The therapist will address any adverse reactions to the cues at that time. In addition, therapists will now see all patients for an additional week of therapy. Thus, a plan is also in place for follow-up with these patients. During this session at week-33, the therapist will assess whether there were any adverse events, including a lapse that may have resulted from the cues. Any adverse events will be addressed in the session and reported to the PI. These procedures ensure that the patient does not leave the lab in a vulnerable state. If more than five individuals during the entire trial report having a lapse within 48 hours of the cue exposure session, we will discontinue the cue exposure assessment.

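### The total alcoholic beverage in the fMRI cue task is stated as 12 ml in two places and 1 ml in a third, all described as under a teaspoon, which cannot hold for 12 ml

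*Combined protocol and SAP*

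**What the plan says.** The cue task compares the taste of the participant's preferred alcoholic drink with that of litchi juice during fMRI, at baseline and week 32. Five places bear on how much of the alcoholic drink is given.

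- **Section IV, MRI Data Collection (Baseline and Week 32).** "the total amount of the alcoholic beverage is only 12 ml (less than a teaspoon". The same paragraph describes "only administering 1 ml of each beverage through Teflon tubing that is attached to a computer controller gustometer, over each 24 second trial" and "a block design with twelve pseudorandomly ordered alcohol and control trials that are presented in two consecutive runs".
- **Section XI, instrument table, Functional MRI row.** Repeats the Section IV text: 12 ml, the teaspoon description, 1 ml per trial and the twelve trials.
- **Section XI, MRI Scan I.** "The total amount of the alcoholic beverage is only 1 ml (less than a teaspoon". The per-trial volume is the same as in Section IV ("Subjects will be administered 1 ml of each beverage through Teflon tubing", again per 24-second trial). No number of trials is given.
- **Section XV, Exposure to Alcohol.** "participants are exposed to less than a teaspoon of an alcoholic beverage". No volume in ml.
- **Section XVI, Exposure to Alcohol.** "the entire task uses less than 1 tsp of an alcohol beverage". No volume in ml.

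Nowhere is it stated whether twelve is the number of trials in all or the number of each type, and nowhere is a teaspoon defined.

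**The concern.** One task has two stated totals, and one household measure is applied to both. The two totals cannot both be right, and the measure cannot describe the larger one.

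This is live text. The 1 ml figure stands in the procedures for the scan visit and the 12 ml figure in the design section and the instrument table, so staff reading different sections get different answers.

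Participants have an alcohol use disorder. Section XV itself says that the craving risk matters most at the second scan, when many may be abstinent or drinking much less. Section XVI offers the small quantity as one of its reassurances. If the delivered total is nearer the larger figure, that reassurance describes less exposure than participants receive.

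**Working it through.** **Inputs from the documents**

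- Stated totals: 12 ml (Section IV and the instrument table) and 1 ml (MRI Scan I).
- Volume per trial: 1 ml of each beverage over each 24-second trial (all three places).
- Trials: twelve alcohol and control trials in two runs (Section IV and the instrument table).

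**Assumptions, not in the documents**

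- Teaspoon of 5 ml, varied from 3.55 to 5.92 ml.
- Where twelve is read as the number of trials in all, an even split into six alcohol and six control.

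**Step 1. Compare the stated totals.** 12 / 1 = 12, a 12-fold difference.

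**Step 2. Test the teaspoon description.** Teaspoons = total in ml / ml per teaspoon.

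| Total | at 5 ml | at 5.92 ml | at 3.55 ml | Under a teaspoon? |
|---|---|---|---|---|
| 12 ml | 2.40 | 2.03 | 3.38 | never |
| 6 ml | 1.20 | 1.01 | 1.69 | never |
| 1 ml | 0.20 | 0.17 | 0.28 | always |

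The plan's pairing of 12 ml with less than a teaspoon is not reproduced at any teaspoon size in the range. Its pairing with 1 ml is.

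**Step 3. Rebuild the total from the task description.** Total = number of alcohol trials × 1 ml.

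- Twelve trials of each type: 12 × 1 = 12 ml, which matches Section IV. The same total follows if every one of twelve trials is read literally as giving 1 ml of both beverages.
- Twelve trials in all, split evenly (assumed): 6 × 1 = 6 ml, which matches neither stated total.
- A total of 1 ml: 1 / 1 = 1 alcohol trial, which is hard to square with a block design of twelve intermixed trials over two runs.

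**Step 4. Find how many alcohol trials the teaspoon wording allows.** At 1 ml per trial and a 5 ml teaspoon, the total stays below a teaspoon with at most 4 alcohol trials (at most 3 at 3.55 ml, at most 5 at 5.92 ml).

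**Step 5. See whether the stated scan time settles the count.** The instrument table lists 6 minutes for functional MRI. Twelve trials take 12 × 24 s = 4.8 minutes; twenty-four take 24 × 24 s = 9.6 minutes. The documents do not say whether the 6 minutes covers one run or both, or whether there are gaps between trials, so this does not fix the count.

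**The case against.** The best reply is that this is a wording slip with little consequence, and much of that stands. The volumes are of beverage, not pure alcohol, and are small on any reading. No hypothesis, endpoint, power calculation or analysis uses them. Under the COVID-19 remote version no MRI data are collected, so the point arises only while scanning takes place.

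Section XVI also does not depend mainly on the quantity. It cites use of the same task in over 600 people without observed adverse effects, an option to decline with a reminder, assessment and time with a therapist before leaving, a week-33 session, and a rule to discontinue the cue task if more than five people report a lapse within 48 hours. None of these changes with the volume.

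A reader might infer three stronger things that the documents do not support:

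- **That the exposure is understated in the risk sections.** Those sections give no volume in ml, and their wording agrees with the 1 ml in MRI Scan I. If 1 ml is right, they understate nothing. The text supports only that they may.
- **That the DSMB relies on the teaspoon statement.** Section XVIII has the DSMB review adverse events and emerging safety differences between arms. It does not mention the stated volume.
- **That the participant information is wrong.** It was not available for this review. Section XVI says that the consent form gives the timing of the cue session and the right to opt out, not that it gives a quantity.

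The reply does not remove the contradiction. Three complete statements of one quantity disagree, two of them contradict their own description, and nothing elsewhere reconciles them.

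**Conclusion.** Wrong as written. The stated totals differ 12-fold, and the teaspoon description is false for 12 ml at every teaspoon size tried (2.0 to 3.4 teaspoons; 2.4 at 5 ml). The 1 ml total fits the description but implies a single alcohol trial at the stated volume per trial. The assumed even split gives 6 ml, which fits neither total and is also over a teaspoon (1.01 to 1.7; 1.2 at 5 ml).

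The 12-fold difference rests on the documents alone. The teaspoon equivalents need the assumed teaspoon size, although the conclusion for 12 ml does not turn on it. The 6 ml figure needs the assumed split.

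Which total is right cannot be determined from the documents. It follows that the exposure described in Sections XV and XVI may be understated, and no more than that. The statistical content of the plan is untouched.

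**What to change.** Reconcile the five places: MRI Data Collection in Section IV, MRI Scan I and the Functional MRI row of the instrument table in Section XI, and Exposure to Alcohol in Sections XV and XVI.

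- State the number of alcohol trials and the number of control trials per scan session, the volume per trial, and one total that agrees with them.
- Make the teaspoon wording match the reconciled total wherever it appears, or replace it with the volume in ml.
- Check whether the participant information repeats a volume or the teaspoon description, and align it if it does.

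The sponsor must supply what the task delivers; no volume or number of trials is proposed here. The cost is a wording amendment to the protocol, and to the participant information only if the check finds the same statement there. Sample size, endpoints and analyses do not change.

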### **Specific Aim 2.**

#### Examining the putative molecular mechanisms underlying the effects of MBRP versus RP.

- Hypothesis 2. Based on studies suggesting that MBIs alter epigenetic regulation of key genes implicated in alcohol dependence (i.e., DRD2, SLC6A3, DBH) and reduce inflammatory pathway activation (i.e., IL-8, IL-6, TNF $\alpha$ ), it is hypothesized that MBRP treatment will demonstrate significant decreases in methylation of key genes as well as decreases in inflammation biomarkers.
- Hypothesis 3. It is also hypothesized that individuals who receive MBRP, as compared to RP, will demonstrate greater LECN/RECN connectivity as well as reduced cue-elicited BOLD response in the striatum.

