### **Specific Aim 3.**

#### The third specific aim will determine whether the effectiveness of MBRP vs. RP on clinical outcomes is mediated by the effect of MBRP on molecular mechanisms, and, in turn, their effects on network connectivity and BOLD response.

- Hypothesis 4. It is hypothesized that the effects of MBRP on clinical outcomes (Hypothesis 1) will accrue through two routes: the effects of MBRP on reductions in inflammatory markers

(Hypothesis 2) which in turn influence LECN/RECN connectivity; and the effect of MBRP on methylation of key genes which in turn influence cue-elicited BOLD activation in the striatum (Hypothesis 3). These effects will be tested in the context of a structural equation modeling framework.

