### **DRD2 Methylation and BOLD Response to Alcohol Cues.**

BOLD response to alcohol cues in the nucleus accumbens and caudate were extracted from each individual in a previously collected data set ( $n=78$ ). Correlations between the BOLD response to alcohol cues in these structures and the average methylation of the 17 CpGs were calculated. Negative correlations were found between the average methylation of the 17 CpGs and the bilateral caudate (left:  $r = -0.273$ ,  $p = 0.027$ ; right:  $r = -0.305$ ,  $p = 0.013$ ) and nucleus accumbens (left:  $r = -0.247$ ,  $p = 0.045$ ; right:  $r = -0.241$ ,  $p = 0.052$ ).

[figure not shown]

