#### **Specific Aim 2 - Detecting Treatment Effects on Molecular Mechanisms.**

The effect of the treatment on methylation and inflammation (HYPOTHESIS 2) will be analyzed with one 2 (**Treatment:** 8 weeks of MBRP vs. 8 weeks of RP) x 5 (**Time:** Baseline, 4, 8, 20, 32 weeks) mixed multivariate general linear model with methylation outcomes of DRD2, SLC6A3, and DBH and a second model with peripheral inflammation outcomes of IL-6, IL-8, and TNF $\alpha$ . The effect of the treatment on cue-elicited BOLD activation and network connectivity (HYPOTHESIS 3) will be analyzed with a 2-way multivariate analysis of variance (MANOVA; **Treatment:** 8 weeks of MBRP vs. 8 weeks of RP) with BOLD activation in the accumbens, caudate, putamen, and anterior cingulate regions as separate outcomes in the same analysis, and a second MANOVA with network connectivity

The image part with relationship ID rid9 was not found in the file.

in the RECN and LECN as the outcomes. Note, again, that FIML estimation will be used to allow full utilization of available data in an intent to treat framework. It is also possible that the treatments are equally effective on drinking outcomes, and thus we will not see a differential effect of treatment on the mediators. Yet it is still important to know whether levels of methylation or inflammation post-treatment have any impact on changes in

neurocognitive outcomes. Thus, the test of Specific Aim 3 is still critical, even in the case that both treatments are equally effective on both the mediators and drinking outcomes.

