2011). It is reliable and well validated. The task compares the taste of an individual's favorite alcoholic beverage with a sweet, appetitive control taste (litchi juice). The task was designed to minimize movement by only administering 1 ml of each beverage through Teflon tubing that is attached to a computer controller gustometer, over each 24 second trial. It is important to note that the total amount of the alcoholic beverage is only 12 ml (less than a teaspoon). The task itself involves a block design with twelve pseudorandomly ordered alcohol and control trials that are presented in two consecutive runs. In order to examine whether the effects of MBRP differ from those of RP, we will calculate the signal change for alcohol minus the control condition in the precuneus, putamen, and anterior cingulate and use the signal in these regions of interest (ROIs) in the structural equation models (see analysis section).

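### The BOLD mediator for the methylation route of Hypothesis 4 covers the striatum only through the putamen and uses a different region set from the Hypothesis 3 test

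*Combined protocol and SAP*

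**What the plan says.** All references are to the combined protocol and SAP.

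- **Objectives, Specific Aim 2, Hypothesis 3.** MBRP, compared with RP, is expected to show "reduced cue-elicited BOLD response in the striatum".
- **Objectives, Specific Aim 3, Hypothesis 4.** There are two routes to the clinical outcome. One runs from inflammation to executive-network connectivity. The other is "the effect of MBRP on methylation of key genes which in turn influence cue-elicited BOLD activation in the striatum".
- **Research Study Design, MRI Data Collection.** The cue-task signal is to be computed "in the precuneus, putamen, and anterior cingulate and use the signal in these regions of interest (ROIs) in the structural equation models". The fMRI entry of the measures table under Procedures repeats the list: "signal change for alcohol minus the control condition in the precuneus, putamen, and anterior cingulate".
- **Data Analysis Plan, Specific Aim 2.** The MANOVA for Hypothesis 3 takes "BOLD activation in the accumbens, caudate, putamen, and anterior cingulate regions as separate outcomes in the same analysis".
- **Data Analysis Plan, Specific Aim 3.** Change in cue-elicited BOLD is a mediator, but no region is named. Methylation, inflammation and drinking outcomes are declared latent; BOLD is not on that list.
- **Preliminary Studies, DRD2 Methylation and BOLD Response to Alcohol Cues.** The pilot data (n = 78) relate methylation to "BOLD response to alcohol cues in the nucleus accumbens and caudate".

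**The concern.** Hypothesis 4 is a chain: treatment, methylation, striatal BOLD, drinking. Hypothesis 3 tests the treatment effect on the BOLD part of that chain. The two aims inform each other only if BOLD means the same thing in both, and the hypotheses say it means the striatum. As written, the SEM leaves out two striatal regions that the MANOVA includes and adds one region that the MANOVA does not have.

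The cost is in interpretation. A null methylation-to-BOLD path could arise because accumbens and caudate were left out. A significant path could be carried by anterior cingulate or precuneus, and would then say little about the striatum. Nor could a Hypothesis 3 result from the MANOVA be read across to the corresponding part of the SEM.

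**Working it through.** The plan states no figure on this point to reproduce. The check compares the region lists.

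**Assumption.** The documents do not define the striatum. I take it as accumbens, caudate and putamen (standard anatomy). The Mechanistic Framework section in the Background lists striatum, anterior cingulate and precuneus as separate structures, so in the plan's own terms the last two are not striatal.

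| Region | Striatal | SEM (Hypothesis 4) | MANOVA (Hypothesis 3) | Pilot methylation-BOLD correlation |
|---|---|---|---|---|
| Accumbens | yes | no | yes | left -0.247, right -0.241 |
| Caudate | yes | no | yes | left -0.273, right -0.305 |
| Putamen | yes | yes | yes | none reported |
| Anterior cingulate | no | yes | yes | none reported |
| Precuneus | no | yes | no | none reported |

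**Counts from the table**

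- In both lists: putamen and anterior cingulate, 2 regions. Distinct regions overall: 3 + 4 - 2 = 5.
- SEM only: precuneus. MANOVA only: accumbens and caudate.
- Striatal share: 1 of 3 in the SEM, 3 of 4 in the MANOVA.
- SEM regions with a pilot methylation-BOLD correlation: 0 of 3. All four reported correlations come from the two regions that the SEM omits.

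**Sensitivity to the assumption.** Because the plan itself sets anterior cingulate and precuneus apart from the striatum, the SEM share cannot exceed 1 of 3 under any definition consistent with the Background.

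**How the regions enter the model.** The MRI section refers the reader to the analysis section. The only BOLD region list there is the MANOVA's, which differs. The Aim 3 text does not say whether the regions are averaged, modelled as separate mediators or treated as indicators of one factor. If the three SEM regions were simply averaged (my assumption, for illustration), the putamen would carry 1/3 of the weight, and 2/3 would come from regions that the hypothesis does not name.

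**Power.** The Aim 3 power section assumes d = .30 for the epigenetics-to-BOLD relation and gives power of .87 for the smallest path with 226 participants. It names no BOLD region and does not say that the value was taken from the pilot correlations. The mismatch therefore does not show the power figure to be wrong. It does mean that the figure is not tied to a defined mediator.

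**The case against.** **The SEM list has a rationale.** The Background describes the reward network through striatum, anterior cingulate and precuneus, and says this agrees with the team's own imaging work. Putamen, anterior cingulate and precuneus supply one region for each. This stands: the list is not arbitrary. But it represents a reward network, and the hypotheses name only the striatum.

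**A reader might infer that the mediation model does not test Hypothesis 4 at all.** The documents do not support that. The putamen is striatal, so the methylation route is tested in part, and the inflammation-to-connectivity route does not depend on the BOLD regions.

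**A reader might infer that the two lists are unrelated.** They share putamen and anterior cingulate.

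**A reader might infer that two lists leave the regions to be picked after the data are seen.** Each list is written in advance and assigned to a named analysis, so that is too strong. What is open is how the regions are combined in the SEM.

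**A reader might infer that the omitted pilot regions show the SEM regions to be unrelated to methylation.** The pilot section reports extraction from accumbens and caudate only. For the other three regions there is no report either way.

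**Other remedies exist.** The hypotheses could be reworded to the reward network instead. That would also remove the contradiction, but it would change the hypothesis to fit the list and leave the only regions with pilot data outside the SEM.

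**Conclusion.** The point holds in a limited form. The BOLD mediator specified for the methylation route of Hypothesis 4 does not match the hypothesis or the Hypothesis 3 analysis: one of its three regions is striatal, against three of four in the MANOVA, and it omits both regions that have pilot methylation-BOLD correlations. The Aim 3 section neither names the regions nor says how they form a mediator. The SEM therefore tests the striatal route only in part, and on a different construct from the Aim 2 test.

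This rests on the anatomical assumption stated above and on the text of the Aim 3 section. That section also refers to Figure 4, which was not available for this check and may show how BOLD enters the model. The problem is confined to one route of a mechanistic aim. The analysis of heavy drinking days is not touched.

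**What to change.** 1. Name one pre-specified striatal set (accumbens, caudate and putamen) as the BOLD measure for both the Hypothesis 3 MANOVA and the Hypothesis 4 SEM.
2. State in the Aim 3 analysis section how the three regions enter the SEM, for example as their average or as indicators of one latent variable. If latent, add BOLD to the constructs declared latent.
3. Keep anterior cingulate and precuneus as labelled secondary analyses.
4. Make the MRI Data Collection section, the fMRI entry of the measures table, and the Aim 2 and Aim 3 analysis sections agree, before imaging results are examined by arm.

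**Cost.** No new data are needed, since all five regions come from the same cue-task scans. It is more than a wording change, though: the SEM needs a minor respecification, and the d = .30 path assumption and the resulting power should be checked against the revised mediator.
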